3.3 Secondary Study Endpoints

- 1) Determine ECG changes and incidence of arrhythmias after consumption of Adderall compared to baseline ECG
- 2) Determine if consumption of a dose of Adderall is associated with altered neurohormonal and cardiovascular activation, assessed by measurements of biomarkers, such as catecholamines before and after Adderall/placebo intake
- 3) Determine if taking Adderall induces orthostatic changes
- 4) Assess baroreflex sensitivity (paced breathing) before and after Adderall vs placebo intake
- 5) Determine the effect of Adderall on cardiovascular hemodynamics during stress conditions including mental stress (arrhythmics), physical stress (sustained hand grip) and pain stress (cold pressor stress) as compared to measurements at rest
- 6) Determine the changes in heart function and brachial artery reactivity after Adderall intake using ultrasound
- 7) Determine the changes in appetite and food consumption after Adderall vs placebo
- 8) Determine the prevalence of stimulant medication use, history of weight changes and dietary habits among healthy adults (utilizing standard questionnaires).

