7.2 Statistical Methods

Descriptive Statistics

Univariate descriptive statistics and frequency distributions will be calculated, as appropriate for all variables. Baseline values for demographic, clinical, and outcome variables (primary and secondary) will be tabulated for both groups (i.e., study drug vs placebo drug). Data will be inspected before analysis for the need of transformations to reduce the possible impact of outliers in skewed distributions, and transformed accordingly. Distributions across subgroups used in randomization will also be compared to assess whether the randomization was successful in equalizing distributions of these prognostic variables across treatment groups. Putative prognostic variables that will be investigated through these descriptive analyses include variables such as BP, HR, age, gender, BMI, baroreflex sensitivity, catecholamine responses.

Handling of Missing Data

We expect missing data to be minimal. However, some subjects may drop out from the two study day protocol. The two-day longitudinal model is flexible to allow available data to be analyzed, for instance, if a subject completes the first study day, but not second study day. These models assume ignorable (MCAR/MAR) missingness. Sensitivity analyses may be performed to assess the robustness of these assumptions.

Multiplicity

There is no need to account for multiple comparisons in this study. With only 30 subjects, no correction for multiple comparisons using Bonferroni or Tukey's procedure will be necessary.

Primary Hypothesis: We hypothesize that BP and HR increase after intake of study drug compared to placebo.

Data will be analyzed using two-way analysis of variance (ANOVA) for repeated-measures with time (before vs after drug intake) as the within factor and group (study drug vs placebo drug) as the between factor. The key variable will be the group-by-time interaction. Differences in hemodynamics before and after consumption of a drug will be determined by repeated measures ANOVA. Student *t* test (paired or unpaired) will be used for between group comparisons with respect to change in given variable. $P < 0.05$ will be considered statistically significant. Data will be expressed as mean \pm SEM.

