Secondary Hypothesis 1: We hypothesize that study drug will induce more frequent and more severe electrocardiographic findings compared to intake of a placebo drug. We hypothesize that biochemical/metabolic responses to consumption of study drug will be altered after consumption of study drug as compared to placebo drug (ie: increased catecholaminergic response after study drug consumption).

Data will be analyzed using two-way analysis of variance (ANOVA) for repeated-measures with time (before vs after drug intake) as the within factor and group (study drug vs placebo drug) as the between factor. The key variable will be the group-by-time interaction. Differences in electrocardiographic and biochemical/metabolic responses before and after consumption of a drug will be determined by repeated measures ANOVA. Student *t* test (paired or unpaired) will be used for between group comparisons with respect to change in given variable. $P < 0.05$ will be considered statistically significant. Data will be expressed as mean \pm SEM.

Interim Analysis

There will not be any interim analysis.

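### Arrhythmia incidence is a sparse yes/no outcome, but the only methods named for it are ANOVA and the t test with mean ± SEM, which can mislead when events are few

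*Combined protocol and SAP*

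**What the plan says.** Section 3.3 (repeated in Sections 2 and 7.1) gives secondary endpoint 1 as "Determine ECG changes and incidence of arrhythmias after consumption of Adderall compared to baseline ECG". The matching hypothesis in Section 7.2 is that "study drug will induce more frequent and more severe electrocardiographic findings compared to intake of a placebo drug".

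For that hypothesis Section 7.2 prescribes a two-way repeated-measures ANOVA (time by treatment, with the interaction as the key term). It names the ECG data expressly: "Differences in electrocardiographic and biochemical/metabolic responses before and after consumption of a drug will be determined by repeated measures ANOVA". It adds that a Student t "test (paired or unpaired) will be used for between group comparisons with respect to change in given variable". The summary is also fixed: "Data will be expressed as mean" ± SEM.

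Two general clauses in Section 7.2 bear on the point. One is descriptive: "Univariate descriptive statistics and frequency distributions will be calculated, as appropriate for all variables". The other concerns skewness: "Data will be inspected before analysis for the need of transformations to reduce the possible impact of outliers in skewed distributions". The Study Summary and Sections 7.1 and 7.2 name no exact, McNemar, logistic, rank or ordinal method, and no confidence interval for a proportion.

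**The concern.** Whether a subject had an arrhythmia on a given day is a 0/1 variable. The study enrols healthy nonsmokers and excludes known cardiovascular disease and a family history of sudden cardiac death, so few events should be expected. A t test on a handful of ones among 30 values relies on a normal approximation that is poor there, and the SEM of a column of zeros is zero.

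Two misreadings are at stake. A result such as 4 against 0 could be declared significant when a paired exact test would not support it. A day without events could be reported as 0 ± 0 and read as evidence that the drug carries no rhythm risk, in a study that Section 8 rates above minimal risk.

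**Working it through.** **Inputs.** N = 30 (Sections 4.1 and 7.1; Section 3.1 says about 25). Two-sided alpha 0.05 (Section 7.1). Two-period crossover, so each subject has a drug day and a placebo day (Section 3.1). The plan gives no arrhythmia rate and no power figure for this endpoint, so there is no stated figure to reproduce; the 80% power in Section 7.1 is for blood pressure, heart rate and similar measures. The event counts below are therefore illustrative.

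**How sparse?** The nearest rates in the documents are those listed in Section 1.4 for the extended-release form: palpitations 2% to 4%, adult tachycardia up to 6%. At 6%, 0.06 × 30 = 1.8 subjects would be expected.

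**Paired t test on 0/1 data.** Let b subjects have an arrhythmia on the drug day only and none on the placebo day only. The within-subject difference has mean m = b/n and variance s² = (b − n·m²)/(n − 1). For b = 4, n = 30:
- m = 4/30 = 0.1333
- s² = (4 − 30 × 0.01778)/29 = 0.1195, s = 0.3457
- SEM = 0.3457/√30 = 0.0631
- t = 0.1333/0.0631 = 2.11 on 29 df, p = 0.043

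The unpaired version has the same t on 58 df, p = 0.039. If there are no pre-dose events, this equals the p-value of the planned interaction with treatment as a between-subject factor.

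**Exact McNemar test.** p = 2 × 0.5^b (at most 1), and mid-p = p − 0.5^b. For b = 4: 2 × 0.0625 = 0.125, and mid-p = 0.0625.

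| Drug-only vs placebo-only (n = 30) | Paired t | Unpaired t | Exact McNemar | Mid-p McNemar |
|---|---|---|---|---|
| 1 vs 0 | 0.3256 | 0.3215 | 1.0000 | 0.5000 |
| 2 vs 0 | 0.1608 | 0.1555 | 0.5000 | 0.2500 |
| 3 vs 0 | 0.0831 | 0.0779 | 0.2500 | 0.1250 |
| 4 vs 0 | 0.0434 | 0.0390 | 0.1250 | 0.0625 |
| 5 vs 0 | 0.0226 | 0.0192 | 0.0625 | 0.0312 |
| 6 vs 0 | 0.0117 | 0.0093 | 0.0312 | 0.0156 |

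With n = 25 the 4 vs 0 row is almost the same: paired t 0.0429, exact 0.1250.

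**False-positive rate of the paired t test, n = 30.** Given exactly four discordant subjects, the test rejects at 4–0 and 0–4, so the rate is 2 × 0.5⁴ = 12.5%. It is 6.25% given five, 7.0% given eight and 6.5% given eleven. It is 0% given one to three, and 3.1%, 1.6%, 3.9% and 2.2% given six, seven, nine and ten. Averaged over the number of discordant subjects, it is 0.14% when 3% of subjects are discordant, 3.1% at 10%, 4.8% at 20% and 4.3% at 30%.

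**Zero events.** Mean ± SEM is 0 ± 0. The exact two-sided 95% upper limit is 1 − 0.025^(1/30) = 11.6% for 0/30, and 1 − 0.025^(1/25) = 13.7% for 0/25.

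**The case against.** The best defence is that little goes wrong in practice. Overall type I error is below 5%. For one-sided splits, the paired t and exact McNemar verdicts differ only at 4–0 and 5–0, and at 5–0 the mid-p test is also significant (0.031), so that difference reflects the conservatism of the exact test. At the 2 or so events suggested by the 6% rate, neither test is significant. All of this stands. A reader might infer that the plan's p-values are wrong in general or that its error rate is inflated; the calculation does not support that.

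The plan also promises frequency distributions, so 0/30 could appear as a count. That stands too, but a count is not an interval, and the only stated measure of uncertainty remains the SEM.

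A reader might further infer that ectopic-beat counts will lose power under a t test. The documents do not support this: they define no such count, and the clause on transforming skewed data already allows a log-type transformation. No transformation helps a yes/no variable.

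Finally, this is part of one of eight secondary endpoints in a self-described pilot, Section 3.4 disclaims primary safety endpoints, and adverse events are recorded separately. That limits the importance of the point but does not make the stated method suitable.

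**Conclusion.** The point holds for arrhythmia incidence. Section 7.2 assigns a binary endpoint to methods for continuous data and offers no interval for a proportion. The damage is confined to sparse results. A 4 vs 0 outcome changes from p = 0.043 to 0.125 (0.0625 by mid-p), and a day without events is shown with zero standard error when rates up to 11.6% remain compatible with the data.

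This rests on N of about 30, on events being few (plausible, but no rate is given), and on arrhythmia being scored yes/no per day. ANOVA and the t test are suitable for ECG intervals. The primary analysis of blood pressure and heart rate is not touched. The change should be made, but it is not critical.

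**What to change.** In Section 7.2, under Secondary Hypothesis 1:

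- Define the binary outcome as any new post-dose arrhythmia relative to that day's pre-dose ECG. This keeps the baseline comparison in the endpoint's wording.
- Report n/N per treatment day with exact 95% limits, also when a day has no events. Include subjects who completed only one day in this description.
- Compare the two days by an exact or mid-p McNemar test, stating which, with a score or exact 95% interval for the paired risk difference.
- Keep ANOVA and the t test, with the planned transformations, for ECG intervals and other continuous or count measures.
- If severity is graded, define the grade and use a paired method for ordinal data.

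Settle this before unblinding, because at 4 vs 0 the choice of test decides significance.

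**Cost.** SAP wording and a few lines of code; no new data. There will be fewer significant results when events are few: exact McNemar needs at least six discordant subjects (2 × 0.5⁵ = 0.0625, 2 × 0.5⁶ = 0.031). As an illustration, at assumed independent rates of 13% and 2% its power with 30 subjects is about 12%, against 35% for the paired t test. One-day subjects do not enter the paired test, although Section 7.2 intends to use available data, and McNemar makes no adjustment for period. Both limits should be stated.

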7.3 Subject Population(s) for Analysis

All-randomized population: Any subject randomized into the study.

8 Safety and Adverse Events

The overall study risk for this protocol is considered greater than minimal risk.

Consent: Consent will be obtained before initiating study specific procedures. A quiet, comfortable, and private setting for the informed consent process will be provided. The consent process will be explained to the subject, time will be provided to consider all options and when possible the subject will be provided a copy of the consent form well in advance for review at

home. Study staff will consider the subject's likely reading abilities and provide an impartial witness in the informed consent process if necessary. All questions will be answered. Coercion or other undue influences will be avoided through the use of a quiet, comfortable, and private setting away from areas involved in direct clinical practice will be used for the informed consent process. The subject will be told that informed consent can be revisited at any time and consent can be withdrawn at any time without affecting the subject's medical care. The informed consent process will continue throughout the subject's participation in the study and consent will be informally verified on a continuing basis. Significant new information will be given to the subject as it is available.

Safety: While the measurements and interventions proposed in these studies are used frequently and often on a routine basis in our laboratory, there are some risks to some of the measurements and interventions which will be described below:

- The major risk is that of possible side effects of Adderall. The side effects are outlined in the prior sections of this document. As with any medication, allergic reactions are also a possibility. We will enroll only healthy young subjects. This risk potentially induced by Adderall will be minimized by administering short acting form of Adderall and only one time dose. In the event that subjects develop sustained side effects such as elevated BP, elevated HR or other form of arrhythmia that may acutely compromised subject's health, emergent care will be provided by the medical staff.
- To control for behavioral risks, subjects with a history of psychiatric disorders will be excluded from participation.
- Occurrence of any symptoms and/or side effects will be closely monitored during the study period. Subjects will be informed to report any adverse events to the study team and if necessary they will be promptly referred for care.
- Blood draw: The risks of drawing blood via intravenously inserted catheter include pain, bruising, and rarely, infection at the site of the needle stick and at the side of IV catheter. Risks for blood draw may also include light-headedness. All blood samples will be taken with subjects in the supine position, while being very closely monitored for any light-headedness. The amount of blood taken will not exceed the allowed blood draw volume recommended by the Institutional Review Board (IRB) without obtaining hemoglobin level prior to the blood draw.
- Questionnaires: Some of the questions asked in the study questionnaires may make the subject feel uncomfortable. The subject may choose not to answer any questions that make them feel uncomfortable.
- Blood pressure measurements: There are no significant risks related to noninvasive BP measurements other than temporary discomfort when the cuff is inflated.
- Stress tests: When performing stress tests such as sustained handgrip or inserting hand into ice cold water subjects may experience brief periods of discomfort or pain. Some subjects may feel uncomfortable when asked to do mathematical tasks.
- Ultrasound of the heart and arm vessels: When performing ultrasound of the heart subject may feel temporary discomfort as the ultrasound probe is touching the chest wall. Ultrasound of the arm vessels are performed for endothelial function assessment, which entails inflation of BP cuff, to a pressure of 200 mmHg (or 50 mmHg greater than SBP) for 5 minutes. There are no significant risks related to such noninvasive measurements other than temporary discomfort when the ultrasound probe touches the body or when the

blood pressure cuff is inflated. Ultrasound probe will be pressing lightly on subject's body which may cause only temporary discomfort.

Toxicity: It is not anticipated that there will be any toxicologic issues. One time dose of short acting Adderall 25 mg will be administered orally.

Stopping Rules: Subject decision to withdraw from the study; or meeting of any of the exclusion criteria while participating in the study; or emergence of significant subject safety concerns.

8.1 Definitions

Unanticipated Problems Involving Risk to Subjects or Others (UPIRTSO)

Any unanticipated problem or adverse event that meets the following three criteria:

- Serious: Serious problems or events that results in significant harm, (which may be physical, psychological, financial, social, economic, or legal) or increased risk for the subject or others (including individuals who are not research subjects). These include: (1) death; (2) life threatening adverse experience; (3) hospitalization - inpatient, new, or prolonged; (4) disability/incapacity - persistent or significant; (5) birth defect/anomaly; (6) breach of confidentiality and (7) other problems, events, or new information (i.e. publications, DSMB reports, interim findings, product labeling change) that in the opinion of the local investigator may adversely affect the rights, safety, or welfare of the subjects or others, or substantially compromise the research data, **AND**
- Unanticipated: (i.e. unexpected) problems or events are those that are not already described as potential risks in the protocol, consent document, not listed in the Investigator's Brochure, or not part of an underlying disease. A problem or event is "unanticipated" when it was unforeseeable at the time of its occurrence. A problem or event is "unanticipated" when it occurs at an increased frequency or at an increased severity than expected, **AND**
- Related: A problem or event is "related" if it is possibly related to the research procedures.

Adverse Event

An untoward or undesirable experience associated with the use of a medical product (i.e. drug, device, biologic) in a patient or research subject.

Serious Adverse Event

Adverse events are classified as serious or non-serious. Serious problems/events can be well defined and include;

- death
- life threatening adverse experience
- hospitalization
- inpatient, new, or prolonged; disability/incapacity
- persistent or significant birth defect/anomaly

and/or per protocol may be problems/events that in the opinion of the sponsor-investigator may have adversely affected the rights, safety, or welfare of the subjects or others, or substantially compromised the research data.

All adverse events that do not meet any of the criteria for serious, should be regarded as **non-serious adverse events**.

Adverse Event Reporting Period

For this study, the study treatment follow-up period is defined as 4 hours following the last administration of study treatment. The mean elimination half-life for d-amphetamine and l-amphetamine in adults are 10 and 13 hours, respectively. We will continue to monitor the subject until the completion of study protocol each day after ingestion of the drug (anticipating for about 4 hours) in the CRTU. After this time, subjects will be instructed to present to the Emergency Department if within next 24 hours any side effects of Adderall occur. Subjects will also notify the investigators of this study of any side effects.

To ensure the drug is entirely out of the subject's system, we will separate the study visits by at least 5 half-lives (65 hours, approx. 3 days). We will lengthen this interval to be on the safe side to minimum of 5 days between the studies.

Preexisting Condition

A preexisting condition is one that is present at the start of the study. A preexisting condition should be recorded as an adverse event if the frequency, intensity, or the character of the condition worsens during the study period.

General Physical Examination Findings

At screening, any clinically significant abnormality should be recorded as a preexisting condition. At the end of the study, any new clinically significant findings/abnormalities that meet the definition of an adverse event must also be recorded and documented as an adverse event.

Post-study Adverse Event

All unresolved adverse events should be followed by the sponsor-investigator until the events are resolved, the subject is lost to follow-up, or the adverse event is otherwise explained. At the last scheduled visit, the sponsor-investigator should instruct each subject to report, to the sponsor-investigator, any subsequent event(s) that the subject, or the subject's personal physician, believes might reasonably be related to participation in this study.

Abnormal Laboratory Values

The only laboratory value we will obtain prior to initiation of the study protocol is pregnancy test. If positive, subject will be informed of the results and will be excluded from participation in the study.

Hospitalization, Prolonged Hospitalization or Surgery

Any adverse event that results in hospitalization or prolonged hospitalization should be documented and reported as a serious adverse event unless specifically instructed otherwise in this protocol. Any condition responsible for surgery should be documented as an adverse event if the condition meets the criteria for an adverse event.

To follow the safety of our subjects, all subjects will be closely monitored throughout the study days. Any unanticipated medical problems involving risk to subjects or others and adverse events will be addressed by medical staff, will be recorded and reported as indicated.

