According to the drug information as described in UpToDate and Lexicomp, the initial recommended oral dosing for adults with ADHD is 5 mg once or twice daily; increasing daily dose in 5 mg increments at weekly intervals until optimal response is obtained; usual maximum dose is 40 mg daily given in 1 to 3 divided doses per day. The recommended initial oral dose of Adderall for adults with narcolepsy is 10 mg daily; increasing daily dose in 10 mg increments at weekly intervals until optimal response is obtained; maximum dose: 60 mg daily given in 1 to 3 divided doses per day.

The medication does not require renal or hepatic dosage adjustments. Since we are studying healthy young subjects, we expect them to have normal renal and hepatic function.

Relevant pharmacodynamics and pharmacokinetics of Adderall are as follows:

- Duration of action: Tablet: 4 to 6 hours
- Half-life elimination: Adults: d-amphetamine: 10 hours; l-amphetamine: 13 hours
- Metabolism: Hepatic oxidation via cytochrome P450 to 4-hydroxyamphetamine (active) norephedrine (active), and alpha-hydroxy-amphetamine with both active metabolites subsequently oxidized to 4-hydroxy-norephedrine. Cytochrome P450 2D6 is primarily responsible for the formation of 4-hydroxy-amphetamine.
- Time to peak: Adderall: 3 hours.
- Excretion: Urine (highly dependent on urinary pH); excreted as unchanged amphetamine (30%, may range from ~1% in alkaline urine to ~75% in acidic urine), and derivatives of alpha-hydroxyamphetamine (50%)

Adderall is Controlled Substance, C-II. The alert US Boxed Warning states the drug's potential of abuse, stating "Amphetamines have a high potential for abuse. Administration of amphetamines for prolonged periods of time may lead to drug dependence and must be avoided. Particular attention should be paid to the possibility of persons obtaining amphetamines for nontherapeutic use or distribution to others, and the drugs should be prescribed or dispensed sparingly. Cardiovascular events: Misuse of amphetamines may cause sudden death and serious cardiovascular adverse events."

Please see the documents which are attached to the IRB application for complete information on Adderall, as provided by Lexicomp (available via UptoDate).

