8.2 Recording of Adverse Events

At each contact with the subject, the study team must seek information on adverse events by specific questioning and, as appropriate, by examination. Information on all adverse events should be recorded immediately in the source document, and also in the appropriate adverse event section of the case report form (CRF). All clearly related signs, symptoms, and abnormal diagnostic, laboratory or procedure results should be recorded in the source document.

All adverse events occurring during the study period must be recorded. The clinical course of each event should be followed until resolution, stabilization, or until it has been ultimately determined that the study treatment or participation is not the probable cause. Serious adverse events that are still ongoing at the end of the study period must be followed up, to determine the final outcome. Any serious adverse event that occurs after the study period and is considered to be at least possibly related to the study treatment or study participation should be recorded and reported immediately.

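### Late non-serious adverse events can be asked about after dose 1 but not after dose 2, because follow-up ends 4 hours after the last dose

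*Combined protocol and SAP*

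**What the plan says.** Section 8.1 (Adverse Event Reporting Period) says that "the study treatment follow-up period is defined as 4 hours following the last administration of study treatment". The same text expects about 4 h of on-site monitoring on each study day, lasting until that day's procedures are done. After that, "subjects will be instructed to present to the Emergency Department if within next 24 hours any side effects of Adderall occur", and subjects are also to tell the investigators about side effects. Neither instruction is limited to one dose or to serious events. Under Post-study Adverse Event, subjects are to be told at the last scheduled visit to report later events thought to be related to participation.

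Section 8.2 sets the recording rules. On scope: "All adverse events occurring during the study period must be recorded". For events after that period, its explicit requirement covers only serious events that are at least possibly related. On how events are found: "At each contact with the subject, the study team must seek information on adverse events by specific questioning". The term study period is not defined anywhere.

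Section 6.2 lists a Symptoms Questionnaire at visit 2 before dose 2 is given, and no contact after visit 2. Section 6.1 opens by allowing 5 days to 3 months between visits (its last step says within 2 months).

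On the drug, Section 1.2 gives "Time to peak: Adderall: 3 hours" and "Duration of action: Tablet: 4 to 6 hours". Section 8.1 adds: "The mean elimination half-life for d-amphetamine and l-amphetamine in adults are 10 and 13 hours, respectively".

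**The concern.** In a crossover, adverse events should be collected in the same way after each dose, so that treatment and period are not mixed up in the counts. Here the close of follow-up is tied to the last dose only, and visit 2 acts as an unplanned second look at dose 1. A poor night's sleep after dose 1 falls before the close and can be asked about at visit 2. The same event after dose 2 falls after the close and nobody is scheduled to ask.

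At stake is the completeness of the tolerability data in a study that Section 8 rates as greater than minimal risk. The primary result is not at stake.

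**Working it through.** **1. The plan's own figure.** The washout in Section 8.1 uses five half-lives of the slower isomer: 5 × 13 h = 65 h, and 65/24 = 2.7 days. This agrees with the stated 65 h, about 3 days.

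**2. The 4 h limit against the protocol's figures.**
- Peak at 3 h: the period closes 4 − 3 = 1 h after it.
- Action of 4 to 6 h: the period closes at the lower end.
- Fraction remaining by simple first-order decay, ignoring absorption, is 2^(−t/half-life). At 4 h: 2^(−4/10) = 0.76 for d-amphetamine and 2^(−4/13) = 0.81 for l-amphetamine. At 24 h: 0.19 and 0.28.

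These fractions show that later effects are plausible. They do not measure how many events are lost.

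**3. The two doses side by side.**

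| | After dose 1 | After dose 2 |
|---|---|---|
| On-site monitoring | About 4 h, to the end of the day's procedures | Same |
| Later scheduled contact | Visit 2, 5 days to 3 months on | None |
| Active questioning about late events | At visit 2 | None scheduled |
| Spontaneous reporting | Yes | Yes |
| Late non-serious event must be recorded | Yes, if the study period runs to 4 h after the last dose | Not clearly |

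**4. Size of the loss.** Section 5.3 plans 30 subjects in blocks of 6, so about 15 take Adderall second. Let p be the risk of a late Adderall event, and c1 and c2 the probabilities that such an event is captured after dose 1 and dose 2. The documents give neither c1 nor c2.

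Expected captured events = 15·p·c1 + 15·p·c2, out of 30·p. Share lost = 1 − (c1 + c2)/2. With c1 = 1 this is (1 − c2)/2:
- c2 = 1: 0%
- c2 = 0.75: 12.5%
- c2 = 0.5: 25%
- c2 = 0: 50%

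If c1 is below 1, the total loss is larger and the gap between doses, c1 − c2, is smaller.

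**5. Illustration.** Section 1.4 lists insomnia at 12% to 27% for extended-release product. Borrowing that rate for a single short-acting dose is an assumption. It gives 30 × 0.12 = 3.6 to 30 × 0.27 = 8.1 expected cases. At c2 = 0.5 the loss is 15 × 0.12 × 0.5 = 0.9 to 15 × 0.27 × 0.5 = 2.0 cases. At c2 = 0 it is 1.8 to 4.05.

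**6. Effect on a treatment comparison.** Late placebo events in the Adderall-first half are lost in the same way. With c1 = 1, equal sequences and the same c2 under both treatments, both observed risks are multiplied by (1 + c2)/2. Take 12% on Adderall and an assumed 3% on placebo. The true risk difference is 9 points. At c2 = 0.5 it appears as 9 × 0.75 = 6.75 points, and at c2 = 0 as 9 × 0.5 = 4.5 points. The risk ratio stays at 12/3 = 4, because the factor cancels.

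**The case against.** Several points on the other side stand.

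- **Late dose 2 events need not be missed.** A reader might infer that they are. The documents do not support this: Sections 8 and 8.1 ask subjects to report events after either dose, with no seriousness limit. One sentence in Section 8.2 also calls for information on all adverse events to be recorded, without naming a period. The gap is active against passive collection, plus unclear recording rules.
- **Dose 1 capture is not assured either.** Recall may span up to 3 months, subjects who do not return are never asked, and the questionnaire's recall period is not given.
- **A per-dose reading of the 4 h is possible**, since monitoring is described for each day and the study period is undefined. On that reading the formal windows match, and only the questioning at visit 2 differs.
- **The effect is not one-sided.** A reader might infer that only Adderall is under-counted. Placebo in the Adderall-first sequence is affected equally.
- **Events during the stress tests are not lost.** A reader might think so because post-dose testing starts at 3 h. Subjects are monitored until the day's procedures end, so these events are observed even past 4 h.
- **No general adverse event comparison is planned in Section 7**, and Section 3.4 disclaims primary safety endpoints.

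This limits the size of the point but does not remove it. Spontaneous reports depend on the subject acting and on a belief that the drug or the study was the cause. Subjects are blinded, so that filter depends on what they think they took, and equal capture by treatment is itself uncertain. The protocol does not say that non-serious reports made this way enter the adverse event data.

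**Conclusion.** The point holds as uneven ascertainment by period. Late non-serious events after dose 1 can be actively elicited, with imperfect recall. After dose 2 they rest on spontaneous reports that are not clearly required to be recorded. Late events of the treatment given second are therefore likely to be under-counted: Adderall in about 15 subjects, placebo in the other 15.

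The loss of late Adderall events lies between 0% and 50%, taking dose 1 capture as complete, and the documents do not allow it to be placed more closely within that range. Absolute incidence and the risk difference are pulled down. The risk ratio is unchanged only if capture is equal by treatment. The figure of 1.8 to 4.05 lost insomnia cases should not be read as an estimate, since it needs both an extended-release rate and zero passive capture.

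The blood pressure and heart rate analysis is untouched. This is a weakness in the safety data that is worth correcting because correction is cheap.

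**What to change.** Reconcile Sections 8.1 and 8.2:

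- Define the study period, and define one adverse event recording window of equal length after each dose, covering at least the 24 h that Section 8.1 already names.
- Collect events in that window the same way after both doses, for example by the existing Symptoms Questionnaire completed remotely or by one brief next-day contact.
- State that non-serious reports received after a visit are recorded.
- Tabulate adverse events by treatment and by period.

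The cost is protocol wording and about 30 × 2 = 60 short contacts. This concerns recording only. It leaves dosing, observation on site and care instructions as they are.
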